Protocol Number/Title	CASE 6819 A Phase II Study of Intermittent Checkpoint Inhibitor Therapy In Patients With Advanced Urothelial Carcinoma
Study Phase	A Phase II study
Brief Background/Rationale	
Immunotherapy has revolutionized the treatment of patients with aUC. Five checkpoint inhibitors (CPI) (atezolizumab, pembrolizumab, avelumab, durvalumab, and nivolumab) are approved for relapsed/refractory aUC following platinum-based chemotherapy and 2 CPI (atezolizumab and pembrolizumab) are approved for cisplatin-ineligible patients. Duration of therapy required to sustain clinical benefit is unclear; patients are treated indefinitely until intolerable toxicity or disease progression.
 
Clinical trials investigating CPI in melanoma and kidney cancer have shown durable responses in patients who have discontinued therapy for reasons other than disease progression.^{1,2} Similarly, in the CheckMate275 trial of nivolumab in patients with aUC who progressed following platinum-based chemotherapy, 6 patients had sustained responses off therapy (4–12+ weeks).³ Likewise, in the phase 1/2 trial of durvalumab in aUC, a patient who discontinued treatment, unrelated to progression, maintained a response off therapy for >32 weeks.⁴
 
Although generally well tolerated, the indefinite continuation of CPI presents multiple challenges including cumulative toxicities and financial burdens. Novel dosing schedules, early discontinuation considerations, and biomarkers of response are needed to identify patients who can sustain disease regression while off of therapy.

Primary Objective	To assess the efficacy of intermittent CPI therapy, defined as the proportion of patients who remain off therapy for at least 36 weeks
Secondary Objective(s)	
 • To determine the clinical outcome (TFI, ORR, PFS, OS) in advanced urothelial carcinoma with intermittent CPI therapy, at 12 week intervals from when therapy is first held. • To assess response to re-initiation of CPI therapy.
Exploratory Objective(s)	n/a
Correlative Objective(s)	Tissue: Investigate the genomic and immunologic markers of response and resistance to therapy. [See Section 10.2]

	Blood: Investigate the immunomodulatory cell makeup [specifically, lymphocyte PD-1 occupancy, myeloid-derived suppressor cells (MDSC), regulatory T cells (Treg), CD4 and CD8 T Cells, TCR repertoire] at the start of treatment, during the intermittent phase and off treatment. [See Section 10.1]
Sample Size	20 patients that have enrolled into the intermittent arm
Disease sites/Conditions	Advanced urothelial carcinoma
Interventions	A phase II study conducted investigating the use of intermittent CPI therapy in cisplatin ineligible or treatment refractory patients with aUC who respond to therapy. Patients will be treated with CPI therapy for at least 20 weeks as per standard of care (SOC), at which time those with a tumor burden reduction of 10% or greater will suspend CPI therapy. Patients with a documented increase in ≥ 20% tumor burden (RECIST 1.1 PD) will re-initiate CPI. For those patients who continue to have response, they will remain off therapy.

ABBREVIATIONS

CCCC	Case Comprehensive Cancer Center
CRF	Case Report Form
DSTC	Data Safety and Toxicity Committee
FDA	Food and Drug Administration
ICF	Informed Consent Form
IRB	Institutional Review Board
PRMC	Protocol Review and Monitoring Committee
SOC	Standard of Care
CCF	Cleveland Clinic Foundation
UH	University Hospitals
aUC	Advanced urothelial carcinoma
CPI	Checkpoint inhibitor
OS	Overall survival
PFS	Progression free survival
TFI	Treatment Free Interval
ORR	Overall response rate

TABLE OF CONTENTS

1.0 INTRODUCTION

1.1 Background of Advanced Urothelial Carcinoma and Standard Therapies

Bladder cancer is the sixth most common cancer in the US, with an estimated 81,190 new cases in 2018.⁵ While the majority of cases are localized at initial diagnosis approximately 4% will present with *de novo* metastatic disease and another 40% of patients with localized disease will ultimately develop metastasis despite definitive therapy.⁶⁻⁸ Advanced urothelial carcinoma (aUC) has a 5 year mortality rate exceeding 85%.^{9,10}

The standard therapies for the front-line treatment of aUC are cisplatin based combinations, like methotrexate, vinblastine, doxorubicin, and cisplatin (MVAC) and gemcitabine with cisplatin, which demonstrate an overall response rate up to 50%, including approximately 10%–15% complete responses (CRs).^{11,12} Almost half of urothelial cancer patients are unfit for cisplatin-containing chemotherapy due to impaired renal function, poor performance status or comorbidity. Prior to immunotherapy, the alternative option for cisplatin ineligible patients was gemcitabine with carboplatin or gemcitabine with paclitaxel. Outcomes are comparable to cisplatin based therapy with a median overall survival of 9-13 months.^{1,5,6,13,14} Despite initial chemosensitivity, patients are not cured and the outcome of metastatic urothelial cancer after these regimens is poor: median time to progression is only 7 months and median overall survival (OS) is 15 months.^{9,11} Second line chemotherapy has a limited role, but checkpoint inhibitors offer an additional option for patients who have progressed after initial systemic treatment.

1.2 Immunotherapy in Advanced Urothelial Carcinoma

Immunotherapy has revolutionized the treatment of patients with aUC. These therapies reverse innate immune inhibition by blocking programmed death 1 (PD-1), an inhibitory T-cell receptor, as well as targeting the co-inhibitory molecules programmed death ligands 1 and 2 (PD-L1 and PD-L2) expressed on tumor and other cells.^{1,15} The expression of PD-1, PD-L1, and PD-L2 on their respective cells generates tumor resistance to the endogenous immune response resulting in tumor proliferation and growth. Blocking these resistance mechanisms with PD-1, PD-L1, and PD-L2 antibodies has the potential to enhance and unleash the host immune response against the tumor.^{15,16}

Five CPI (atezolizumab, pembrolizumab, avelumab, durvalumab, and nivolumab) are approved for relapsed/refractory aUC following platinum-based chemotherapy and 2 CPI (atezolizumab and pembrolizumab) are approved for cisplatin-ineligible patients. Given its strong phase III data, pembrolizumab has become the default standard of care.

1.2.1 Pembrolizumab

In KEYNOTE-052, 370 patients with treatment naïve aUC were treated with pembrolizumab 200 mg every 3 weeks for up to two years. The average age was 74 years old, including 29% of patients older than 80 years. At a median follow up of 9.5 months, the ORR was 29%, including 7% of patients achieving CR.¹⁷ Long term follow-up at 11.5 months, confirmed an ORR of 28.9% (95%CI 24.3-33.8) with 8.1% of patients achieving a CR. Median duration of response was still not reached and median OS was 11.5 mo

(95% CI 10.0-13.3). In PD-L1 positive tumors (combined positive score ≥ 10), ORR was 47.3% (95% CI 37.7-57.0) and median OS was 18.5 months (95%CI 12.2- NE). Other subgroups that had improved median OS was lymph node only disease (NR, 95%CI 24.0-57.0), ECOG PS 0/1 (13.1 mo; 95% CI 11.0-16.8), and ECOG 2 (9.7 mo; 95%CI 5.7-11.6). The most common any grade treatment related adverse events (TRAE) were fatigue (18.1%) and pruritis (17.8%). Immune related TRAE occurred in 24.6% of patients.¹⁵ Based on these results, the FDA approved pembrolizumab in the front line setting for cisplatin ineligible, treatment naïve patients with aUC.

In KEYNOTE-045, patients with aUC refractory to cisplatin-based therapy were randomly assigned to either pembrolizumab (200 mg every 3 weeks for up to 2 years) versus investigator's choice of chemotherapy (including paclitaxel, docetaxel, or vinflunine). At a median follow up of 27.7 months, pembrolizumab showed improved OS (10.1 vs. 7.3 mo, HR 0.7; 95% CI 0.57-0.85, p< 0.0002), improved ORR (21% vs. 11%), improved duration of response (NR vs. 4.4 mo), less grade ≥ 3 toxicity (17% vs. 50%), and longer time to health-related quality of life deterioration (3.5 vs. 2.3 mo; HR 0.72).^{18,19} There was no PFS benefit. Based on these results, pembrolizumab monotherapy is also approved in cisplatin refractory aUC.

1.2.2. Atezolizumab

IMvigor 210 was designed to investigate atezolizumab in both the front line and second line setting.

In cohort A, 119 cisplatin ineligible patients received atezolizumab 1200 mg every 3 weeks. At a median follow up of 17 months, ORR was 23%, including 9% CR and median OS was 15.9 months. At the time of analysis, median duration of response was not reached yet and 19 of 27 continued to have response.²⁰ 16% of patients experienced grade 3 or higher TRAE. Thus, atezolizumab is approved for front line therapy in platinum-intolerant patients.

In cohort B, 310 patients with metastatic urothelial carcinoma post-platinum treatment showed improved ORR 15% (compared to historical controls ORR 10%; p= 0.0058) regardless of PD-L1 status. Of the 45 responders, 84% had ongoing response at a median follow up of 11.7 months. Grade 3 or higher TRAE occurred in 16% of patients and immune mediated AE were 5% of patients; most notably pneumonitis, liver enzyme abnormalities, rash and dyspnea.²¹ Patients who continued atezolizumab beyond progression had a longer post progression OS (8.6 months) compared to those transitioned immediately to different treatments (6.8 months) and those who did not have further treatment (1.2 months).²² Based on these results, FDA granted accelerated approval for atezolizumab as a single agent as second-line treatment for subjects with locally advanced or metastatic urothelial carcinoma (mUC).

Of note, based on IMVigor 210, a phase III trial, IMvigor 211, randomized 931 patients, who had received platinum-based chemotherapy, to atezolizumab (1200 mg IV every 3 weeks) or to investigator's choice of second line chemotherapy (vinflunine, paclitaxel, or docetaxel). Atezolizumab had similar median OS (11.1 months vs. 10.6 months; p=0.41) and ORR (23% vs. 22%), but less grade 3 or higher TRAE (20% vs. 43%).²³ Atezolizumab remains approved as second line therapy despite these results.

1.2.3 Durvalumab

Durvalumab was explored in a phase I/II study, MED1 4736, which looked at 191 patients with inoperable or metastatic urothelial cancer who had progressed during or after one standard platinum-based therapy. At a median follow up of 5.78 months, ORR was 17.8% (95% CI 12.7-24.0), including 7 patients who achieved CR. The median time of response was 1.41 months and median durable response had not yet been reached. Of note, patients with PD-L1 expression had better ORR (27.6% vs. 5.1%), median PFS (1.5 mo, 95%CI 1.4-1.9 mo) and median OS (18.2 mo, 95%CI 8.1-NE). Additionally, durvalumab was found to be well tolerated with only 6.8% of patients experiencing a grade 3 or more TRAE and 2.1% of patients having grade 3 or more immune TRAE, most notably hepatitis and pneumonitis.⁴

1.2.4. Nivolumab

In Checkmate 032, an open label, multicenter phase 1/2 expansion cohort study in patients with aUC, who had progressed after previous platinum based therapy, showed nivolumab was associated with a substantial and durable clinical response. At a minimum follow up of 9 months, 19 of 78 (24.4%) of patients had an objective response, with 17.9% achieving CR. The median duration of response was 9.4 months (IQR 5.7-12.5) and the median time to response was 1.5 months (IQR 1.2-4.1). Interestingly, four patients were able to sustain response after nivolumab monotherapy discontinuation (7-22+ weeks).²⁴

In the phase II CheckMate 275 trial, 265 previously treated aUC patients were treated with nivolumab 3 mg/kg IV every 2 weeks until progression or unacceptable toxicity. The ORR was 19.6%. (95% CI 0-24.9) with 2% of patients achieving a CR. The median duration of response was NR, with 77% of patients having an ongoing response and the median OS was 8.74 mo (95% CI 6.05 to NR).³

1.2.5 Avelumab

Avelumab is another PD-L1 inhibitor that has shown benefit in the platinum-refractory space. In a phase 1b trial, avelumab 10mg/kg IV every 2 weeks. At a median follow up of 16.5 months, ORR was 18.2% (95%CI 8.2%-32.7%) with 5 CR. The median duration of response was NR (95%CI 12.1 weeks to NE) and responses were ongoing in 6 patients (75.0%). Of note, 7 of 8 of the responders were PD-L1 positive (IHC \geq 5% of tumor cells). There was also an improvement in median PFS (11.6 weeks, 95% CI, 6.1 to 17.4 weeks), median OS (13.7 months, 95% CI, 8.5 months to NR), and 12-month OS rate (54.3%, 95% CI, 37.9% to 68.1%).²⁵ Based on a pooled analysis of the two expansion cohorts in the above JAVELIN solid tumor trial, avelumab was approved for the treatment of platinum refractory aUC based on a pooled analysis of two expansion cohorts in the above JAVELIN solid tumor trial.²⁶

1.3 Rationale

An unanswered question with the use of CPI is the duration of therapy required for optimal clinical benefit. In the absence of progressive disease or unacceptable toxicities, there are currently no specified criteria for treatment discontinuation. Strategies to reduce toxicity and maximize benefit require investigation. Clinical trials investigating CPI in melanoma and kidney cancer have shown durable responses in patients who have

discontinued therapy for reasons other than disease progression.^{16,27,28} In fact, our group conducted a phase II trial of intermittent nivolumab in aRCC and showed not only was it feasible but that at 48 weeks, 4 out of 5 patients were able to sustain response off therapy.²⁸

Similarly, in bladder cancer, in Checkmate 032, four patients were able to sustain response after nivolumab monotherapy discontinuation (7-22+ weeks).²⁴ Additionally, in the CheckMate275 trial of nivolumab in patients with aUC who progressed following platinum-based chemotherapy, 9 patients had sustained responses off therapy 2-17+ weeks.³ Likewise, in MEDI 4736, there was a patient who discontinued treatment, unrelated to progression, and maintained a response for >32 weeks.⁴

In general, most patients can achieve a response to any of the 5 approved CPI therapies within 2 months of treatment initiation (range 1.4-2.85 months).^{3,4,17,19,21,23-26} Specifically with pembrolizumab, in both cisplatin refractory and cisplatin ineligible patients, the median response time to response was 2-2.1 months and the percentage of patients who responded to pembrolizumab and did not have PD at 1 year was 68% (median duration of response was 1.6+- 30.3+ months.).^{17,19,29} Phase I data in refractory solid tumors showed that regardless of dose, a single IV infusion of nivolumab (0.3-10mg/kg IV) lead to a serum half-life of 12-20 days with a mean plateau PD-1 receptor occupancy on peripheral blood circulating T cells of 72% (range 59-81%) for greater than 57 days.¹⁶ Similar findings were seen in cohort A of a study of melanoma, RCC, and UC, where responders (RECIST CR, PR or SD) had sustained PD-1 receptor occupancy (>80% for up to 300 day) despite non-detectable serum nivolumab levels.³⁰ A review of the pharmacodynamics of all 5 CPI show a flat exposure to response relationship with >70% target receptor saturation (range 70%-99%).³¹ This data suggests that nivolumab has a high affinity for PD-1 and that sufficient concentrations persist to maintain plateau occupancy even when serum levels are not detectable. These studies suggest that those who respond to checkpoint inhibitor therapy do so quickly and potentially could have durable responses.

Along with physical toxicity, financial toxicity is a real concern for treatments with an indefinite time course. The average cost of one dose of any CPI therapy is \$8,791.60, with a yearly cost ranging from \$169,911 to \$200,865.³² These values do not account for the cost of toxicity management that may incur. In an era of health-care cost containment and documented financial burden of cancer therapy to patients and the health-care system, it is particularly important to develop treatment regimens and schedules that reduce cost.

Thus, novel dosing schedules, early discontinuation considerations, and biomarkers of response are needed to identify patients who can sustain disease regression while off of therapy. Similar to the RCC study we previously conducted, we hypothesize that there is a subgroup of patients with advanced urothelial carcinoma who are able to sustain response off of CPI therapy.

1.4 Background and rationale of correlative studies

Immunotherapy functions to modulate the immune microenvironment. Myeloid derived suppressor cells (MDSC), CD8⁺ and CD4⁺ T cells, regulatory T cells (Tregs), T cell receptor (TCR) repertoire, among others are important contributors both to the

function of and resistance to targeted therapy and immunotherapy.³³⁻³⁶ For example, in melanoma, patients with higher numbers of circulating T_{reg} cells and T_{eff} cells after CPI therapy were predictive of treatment responses.^{37,38} CPI therapy was also associated with changes to the TCR repertoire, which is crucial to T cell functioning.³⁹ Additionally, in breast and colon cancer, MDSC levels have correlated with treatment response, disease progression, and clinical outcomes.³⁴ Specifically in urothelial carcinoma, MDSCs in peripheral blood have been correlated with pathology and response to CPI therapies.^{40,41}

The tumor microenvironment as well as the peripheral blood are dynamic and subject to change based on changes in tumor burden and therapy. There is a lack of prospective data demonstrating correlations between changes in peripheral blood and changes in the tumor microenvironment. The goal of this study is to generate a hypothesis that changes in the type and behavior of immunomodulatory cells in the peripheral blood will reflect tumor burden and that such changes will impact tumor burden while on CPI therapy. The presence of a biomarker (or composite biomarker score) to identify patients likely to benefit from CPI will help prospectively select patients for therapy. Likewise, the development of biomarkers to determine which patients are likely to tolerate extended breaks from therapy without compromising efficacy, will minimize toxicity for select patients.

Another point of interest would be to evaluate the rate at which the PD-1 receptor occupancy on peripheral blood circulating T cells changes over time with CPI suspension. Previous studies have shown PD-1 receptors can remain occupied for >10 months despite non-detectable levels in the blood.³¹ This is potentially a reason why patients have “durable” responses and slow resolving toxicities to immunotherapy even after discontinuation. Understanding the pharmacodynamics of anti-PD-1/anti-PD-L1 therapy on PD-1 receptor occupancy is crucial in developing a dose suspension schedule.

Based on our current knowledge these are the correlative we are interested in and will pursue as long as it is still clinically relevant.

2.0 OBJECTIVES

2.1 Primary Objective

To assess the efficacy of intermittent CPI therapy, defined as the proportion of patients who remain off therapy for at least 36 weeks

2.2 Secondary Objective(s)

[figure not shown]
- To determine the clinical outcome (TFI, ORR, PFS, OS) in advanced urothelial carcinoma with intermittent CPI therapy.
- To assess response to re-initiation of CPI therapy

2.3 Correlative Objective(s)

- Tissue: Investigate the genomic and immunologic markers of response and resistance to therapy.
- Blood: Investigate the immunomodulatory cell makeup [specifically, lymphocyte PD-1 occupancy, myeloid-derived suppressor cells (MDSC), regulatory T cells (Treg), CD4 and CD8 T Cells, TCR repertoire] at the start of treatment, during the intermittent phase and off treatment

3.0 STUDY DESIGN

3.1 Study design including dose escalation / cohorts

¹Patients may be treated with any FDA-approved CPI for cisplatin-ineligible aUC or cisplatin resistant/refractory aUC.

²In cases where a patient is continued on therapy after PD and develops subsequent disease progression, CPI should be discontinued.

³Patients who do not have tumor burden reduction of >10% after 2 consecutive imaging will be removed from study.

* Of note all imaging is compared to scans done prior to intermittent therapy initiation.

A phase II study design to investigate the use of any CPI on an intermittent dosing schedule. Patients with aUC who treatment refractory or cisplatin ineligible will receive CPI of choice as per standard dosing. Patients who have initial $\geq 10\%$ tumor burden

reduction will discontinue the CPI until they experience a $\geq 20\%$ disease progression, at which time CPI therapy will be restarted.

The 10% cut off was chosen on the basis of a metanalysis in CPI-treated metastatic melanoma that this cut point may optimally separate overall survival in patients (better than the traditional RECIST PR 30% cut off) and also from prior experience using this cut off in an intermittent nivolumab trial in kidney cancer.^{28,42} Please refer to section 14.0 for statistical consideration, including early stopping rules.

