3.3 Expected Duration of Treatment and Subject Participation

Each study cycle consists of 14-28 days, depending on which CPI is chosen. CPI of choice will be administered on day 1.

All patients who do not meet criteria for the CPI intermittent phase of the study will be treated until unacceptable toxicity or RECIST-defined PD. Patients with RECIST-defined PD may continue CPI therapy at the discretion of the treating MD. These patients will continue with normal imaging every 12 weeks. In cases where a patient is continued on therapy after PD and develops subsequent PD ($\geq 20\%$ increase in sum of target lesions compared to the initial PD tumor measurements, the patient will come off study).

Patients who meet criteria for the intermittent phase (i.e., have $\geq 10\%$ tumor burden reduction) will not receive CPI therapy. Imaging will continue per protocol (every 12 weeks from the initial date they stopped CPI therapy). Patients who have RECIST defined PD on the intermittent phase should reinitiate CPI therapy. Patients who have a subsequent decrease in tumor burden $\geq 10\%$ can then restart CPI therapy as per protocol. (refer to schema in Section 3.1).

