6.4 Criteria for Removal from Study

Patients will be treated per protocol until:

1. RECIST-PD (treating MD may continue CPI). Study PI must be informed via email (or Site Communication Form") that subject is continuing based on clinical benefit. These patients will continue per normal imaging schedule (every 12 weeks).
2. Patients on CPI treatment who develop a RECIST-PD (PD1) can continue CPI treatment if there is clinical benefit. If on subsequent imaging they continue to have RECIST-PD (PD2), they will be removed from trial.
3. Unacceptable toxicity (see Section 7.3)
4. Withdrawal of consent
5. General or specific changes in the patients' condition that render the patient unacceptable for further treatment in the judgment of the investigator.
6. Any patient who on consecutive imaging (i.e., for 24 weeks) has SD while on therapy and does not achieve > 10% tumor burden reduction will be removed from the trial.

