12.0 MEASUREMENT OF EFFECT

Patients must have measurable disease at screening and will be evaluated for response on the basis of RECIST criteria version 1.1.⁴⁴ Tumor measurements using physical examination, spiral CT scan and/or MRI or other appropriate techniques deemed suitable by the investigator will be performed at screening within 28 days of patient registration and repeated per study calendar (Section 11.0) Scans can be done more frequently per MD discretion; these scans will be submitted on an unscheduled disease assessment.

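### The 3.1 footnote fixes the imaging comparator before suspension, while restart is at RECIST 1.1 PD; followed literally, it calls target-lesion PD late in patients who shrink further off therapy

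*Combined protocol and SAP*

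**What the plan says.** Section 3.1, asterisked note under the schema: "Of note all imaging is compared to scans done prior to intermittent therapy initiation". It does not say which scan is meant and makes no exception.

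The restart rule is written elsewhere in RECIST terms:

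- Synopsis, Interventions: "Patients with a documented increase in ≥ 20% tumor burden (RECIST 1.1 PD) will re-initiate CPI".
- Section 3.3: "Patients who have RECIST defined PD on the intermittent phase should reinitiate CPI therapy".
- Section 12.0: patients "will be evaluated for response on the basis of RECIST criteria version 1.1".

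Section 3.3 uses a further comparator for patients treated past a first PD: an "increase in sum of target lesions compared to the initial PD tumor measurements".

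The 10% rules name no comparator. The synopsis gives the point after at least 20 weeks of CPI "at which time those with a tumor burden reduction of 10% or greater will suspend CPI therapy", and section 6.4 item 6 says that a patient with stable disease on therapy who "does not achieve > 10% tumor burden reduction will be removed from the trial".

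Three things use the off-therapy PD call: the restart decision, the 24-week PD count that drives Table 1 (14.2), and the 36-week endpoint (time off therapy in 2.1, sustained response in 14.3).

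**The concern.** RECIST 1.1, as the standard adopted in 12.0, measures target-lesion PD from the smallest sum recorded on study, including sums reached after suspension. A comparator fixed before suspension never moves down. Section 3.3 uses the term intermittent phase for the period off CPI, so the most natural reading of the note is the last scan before suspension.

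On that reading, a patient who shrinks further off drug and then regrows meets the restart rule in the synopsis and 3.3 while the note still shows no progression. Two sites could classify the same patient in opposite ways. The patient read under the note stays untreated, is not counted against the safety boundary, and may count as a success at 36 weeks. All three consequences favor suspension.

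**Working it through.** **Inputs.** PD at a 20% increase (synopsis); scheduled off-therapy scans every 12 weeks (3.3); 20 patients and a 95% CI half-width of at most 0.23 (14.3); beta(0.4, 0.6) prior, with stopping if P(PD rate > 0.4 | data) > 0.85 (14.2). The smallest-sum reference is the RECIST 1.1 definition. The protocol does not write it out.

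**The plan's own figures first.** The largest exact 95% half-width with 20 patients is 0.228, which agrees with 0.23. The beta-binomial rule reproduces every Table 1 boundary from 6 to 19 patients. An exact recursion gives stopping probabilities of 0.120, 0.343, 0.646 and 0.883, against 0.12, 0.34, 0.65 and 0.88 in Table 2. No stated figure is in dispute; the question is which PDs enter them.

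**Thresholds.** Let S be the sum at suspension and s the further proportional shrinkage off therapy, so the smallest sum is S(1 − s).

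- RECIST 1.1 calls PD at 1.2 × S(1 − s).
- The note, read as the last scan before suspension, calls PD at 1.2 × S.
- Regrowth from the smallest sum that the note requires: 1.2/(1 − s) − 1.

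| Further shrinkage s | Regrowth required by RECIST 1.1 | Regrowth required by the note | Sums on which the rules disagree, as % of S |
|---|---|---|---|
| 0% | 20% | 20% | none |
| 10% | 20% | 1.2/0.9 − 1 = 33% | 108 to 120 |
| 20% | 20% | 1.2/0.8 − 1 = 50% | 96 to 120 |
| 30% | 20% | 1.2/0.7 − 1 = 71% | 84 to 120 |

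The smallest sum can never exceed S, so the note is never earlier than RECIST. The error has one direction.

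**Illustrative patient.** 70 mm at suspension, 50 mm at week 12, 65 mm at week 24.

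- RECIST 1.1: 65/50 − 1 = +30%, above the 60 mm threshold. PD, restart, counted in Table 1.
- The note: 65/70 − 1 = −7%, below the 84 mm threshold. No PD. The patient stays off CPI and, if still under 84 mm with no other progression at week 36, counts as a success.

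**When it can happen.** On scheduled scans, a lower sum must be recorded at week 12 to hide a week-24 PD, and at week 12 or 24 to hide a week-36 PD.

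**Effect of one patient.** On the primary proportion, 1/20 = 5 points. On the safety rule at six patients:

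- 4 PDs of 6: posterior beta(4.4, 2.6), P(rate > 0.4) = 0.89 > 0.85, stop.
- 3 PDs of 6: posterior beta(3.4, 3.6), P(rate > 0.4) = 0.67, continue.

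A single uncounted PD can therefore reverse a stopping decision.

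**The case against.** The case on the other side is substantial.

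- **Scope.** The sentence is a note to a schema that is not in the available text, so the asterisk may belong to one box only. Elsewhere the protocol uses intermittent CPI therapy for the whole strategy, and the note speaks of scans in the plural. Section 3.3 already departs from it for PD after PD. This stands: the reach of the note is uncertain.
- **Operative text.** The restart instructions all say RECIST, and a site might simply follow them. That is possible, but nothing reconciles the note with them, and the note says all imaging.
- **Frequency.** Section 1.3 says that responders respond quickly, usually within about 2 months, and patients here have had at least 20 weeks of CPI. Section 1.4 states "Previous studies have shown PD-1 receptors can remain occupied for >10 months despite non-detectable levels in the blood", but uses this to explain durable responses. It makes further shrinkage off drug plausible and does not report any. The disagreement window is narrow when further shrinkage is small, and section 11 also asks for imaging when progression is suspected. This stands too.

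Four stronger readings are tempting and are not supported:

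- A reader might infer a definite loss of stopping probability below the 0.88 in Table 2. That needs the share of week-24 PDs left uncounted, and the documents give no basis for one.
- A reader might take the comparator as the pre-CPI scan and conclude that PD is delayed for everyone suspended. The wording does not exclude that scan, but nothing adopts it, and PD by new lesions would not be delayed under either reading.
- A reader might argue that one scan could trigger both restart and a new suspension. Section 3.3 puts restart first and a subsequent decrease after it, so a scan showing growth does not qualify.
- A reader might say the first 10% reduction cannot be measured, because the scan before suspension would be its own baseline. Placing the reduction after at least 20 weeks of CPI implies change since CPI began. The missing comparator there needs clarifying and is not a second contradiction.

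**Conclusion.** The concern holds as a conflict between a stated comparator and the adopted response criteria. It should be fixed; confidence is moderate. Read as the last scan before suspension, the note delays target-lesion PD in patients who shrink further off therapy and then regrow, with the required regrowth rising from 20% to 33, 50 or 71% after 10, 20 or 30% further shrinkage. With no further shrinkage the two rules agree.

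The conclusion rests on that reading of the note, on its applying to off-therapy scans, and on the RECIST 1.1 smallest-sum definition. How often it would matter is unknown. For scale, the 5 points from one patient compare with a CI half-width of up to 23 points: modest against the sampling error, but always in the direction that makes suspension look better. The sharper exposure is in the early safety looks, where one PD can separate stopping from continuing.

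**What to change.** Replace the note in 3.1 with named comparators, and repeat them in 3.3, 12.0, 14.2 and 14.3.

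1. **Off-therapy PD, restart, the Table 1 count and the 36-week endpoint:** RECIST 1.1 PD, with target lesions measured from the smallest sum on study, including scans taken off therapy.
2. **First 10% reduction (clarification):** change from the last scan before the current CPI course. Eligibility requires at least 20 weeks of CPI, so the screening scan need not be a pre-CPI scan.
3. **Re-suspension (clarification):** change from the scan at which CPI was restarted, taking the 3.3 sentence on a later decrease to mean a second suspension.

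The cost is wording plus one case report form field for the pre-CPI sum, taken from existing scans. Sample size, Table 1 boundaries and imaging schedule do not change. There are two downsides. The 36-week proportion may come out slightly lower because some PDs are called earlier. A few patients may have no retrievable, measurable pre-CPI scan and could not be classified for suspension.
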